6.3. Study Phase (Weeks 1 to Week 24)

Interim safety visits will be scheduled for Weeks 1, 2, 4, and 8. Subjects will visit the NIH CC as outpatients and the following procedures will be conducted:

1. Physical exam and interval medical history, including blood pressure check
2. Research blood collection (fasted overnight) for acute care, hepatic, and mineral panels, , and serum, plasma, and PBMCs for storage. CD4/8 and HIV viral load counts will be done at week 4.
3. Urine pregnancy test for subjects of childbearing potential
4. Pill count of unused study drug to assess adherence

Another outpatient visit to the NIH CC will be scheduled for Week 12. The following procedures will be conducted:

1. Physical exam, including blood pressure check, and interval medical history
2. Research blood collection (fasted overnight) for acute care, hepatic, and mineral panels, lipid profile, CBC, HgbA1c, CD4/8 count, HIV viral load, aldosterone, plasma renin activity, inflammatory markers and adipokines (MCP-1, CRP, adiponectin, PAI-1, resistin, TNF- α , TNFR2, IL-6), SHBG, total and free testosterone, LH (female only), FSH (females only), estradiol (females only), and serum, plasma and PBMCs for storage
3. Urine pregnancy test for subjects of childbearing potential

At week 18, subjects will return to the NIH CC or can choose to go to their local medical provider (if this does not incur additional burden), for the following procedures:

1. Interval medical history, including blood pressure check
2. Research blood collection (fasted overnight) for acute care, hepatic, and mineral panels.
3. If this visit is done by their local medical provider , we will request the results to include in the patient's NIH record.

6.4. Final Study Visit (Week 24)

Subjects will return to the NIH CC for a final study visit at Week 24, after the full regimen of eplerenone has been completed. The following procedures will be conducted:

1. Interval medical history and physical exam, including blood pressure check
2. Bionutrition: DEXA, anthropometric measurements
3. Research blood collection (fasted overnight) for acute care, hepatic, and mineral panels, CBC, lipid profile; HgbA1c, CD4/8 count, HIV viral load, aldosterone, plasma renin activity, inflammatory markers and adipokines (MCP-1, CRP, adiponectin, PAI-1, resistin, TNF- α , TNFR2, IL-6), SHBG, total and free testosterone, LH (female only), FSH (females only), estradiol (females only), and serum, plasma, and PBMCs for storage
4. Urine pregnancy test for subjects of childbearing potential
5. MRI for cardiac and hepatic steatosis and visceral fat volume
6. FibroScan transient elastography
7. Liver biopsy (optional)

6.5. Follow-up End of Study visit (optional)

Subjects may be asked to return for assessments following their week 24 to determine if there are changes in their health status after withdrawal of study medication. These follow up evaluations could include:

1. Interval medical history, including blood pressure check
2. Research blood collection (fasted overnight) for acute care, hepatic, and mineral panels, CBC, lipid profile; HgbA1c, CD4/8 count, HIV viral load, aldosterone, plasma renin activity, inflammatory markers and adipokines (MCP-1, CRP, adiponectin, PAI-1, resistin, TNF- α , TNFR2, IL-6), SHBG, total and free testosterone, LH (female only), FSH (females only), estradiol (females only), and serum, plasma, and PBMCs for storage
3. Urine pregnancy test for subjects of childbearing potential
4. MRI for cardiac and hepatic steatosis and visceral fat volume
5. FibroScan transient elastography

6.6. Early Termination Visit

If a subject's participation is terminated before the end of the study, then they will be asked to come to the NIH CC for a Termination Visit. Laboratory tests and study evaluations to be conducted at that visit will be determined on the basis of the subject's health, their willingness, and the appropriateness of the test at that time point.

6.7. Pregnancy and Follow-up Visit

If a subject becomes pregnant during the course of participation, then their participation in the study will be stopped. The study team will ask the subject to notify them of the pregnancy outcome.

7. Potential Risks and Benefits

7.1. Potential Risks

Eplerenone: In one clinical trial, the overall incidence of AEs reported in patients treated with eplerenone was similar to those treated with placebo.³⁵ The AEs that occurred more frequently in eplerenone-treated patients were hyperkalemia (3.4% with eplerenone vs. 2.0% with placebo) and increased creatinine (2.4% with eplerenone vs. 1.5% with placebo). Discontinuation of

treatment as a result of hyperkalemia or abnormal renal function was less than 1.0% in both groups.

In another clinical trial, the overall incidence of AEs reported in patients treated with eplerenone was also similar to those treated with placebo.³⁵ The AEs occurred at a similar rate in both groups regardless of age, gender, or race. Therapy was discontinued as the result of an AE in 3% of patients treated with eplerenone and 3% of patients given placebo. The most common reasons for discontinuation of eplerenone were headache, dizziness, angina pectoris/MI, and increased concentration of gamma glutamyl transferase. Gynecomastia, mastodynia and abnormal vaginal bleeding were reported with eplerenone but not with placebo. The rates increased slightly with increasing duration of therapy.

Angioneurotic edema and rash have been reported from post-approval use of Inspra.³⁵

There may be additional risks of eplerenone that are currently unknown.

DEXA Scan: The total amount of radiation exposure from 2 DEXA scans is 0.00006 rem. The radiation exposure in this study is below the limit of 5 rem per year allowed for adult research subjects by the NIH Radiation Safety Committee. There is no direct evidence that radiation exposure at this level is harmful, but, as with all radiation exposure, there may be a very slight increase in the risk of cancer.

The average person in the United States receives a radiation exposure of 0.3 rem per year from natural sources, such as the sun, outer space, and the earth's air and soil. A copy of the pamphlet, "An Introduction to Radiation for NIH Research Subjects," will be provided to subjects by request.

Liver Biopsy: Ultrasound-guided percutaneous liver biopsy will be performed by trained interventional radiologists who specialize in gastrointestinal procedures at the NIH. Subjects will be observed as outpatients following liver biopsy per standard of care for liver biopsy and conscious sedation when used. The risks associated with liver biopsy include pain, transient hypotension (vasovagal response), bleeding, and transient bacteremia. Subjects with any contraindication to liver biopsy, including platelets < 75,000, elevated PT or PTT, (except patients with known lupus anticoagulant antibody and aPTT mixing study that is normal at one hour), or chronic aspirin use that cannot be suspended will not undergo biopsy. Individuals on aspirin for primary prevention of MI may undergo biopsy after discontinuation of aspirin for ≥ 7

days. Subjects will receive teaching and instructions for post-biopsy care and will be asked to call or return to clinic with persistent pain or other concerning symptoms.

Conscious Sedation: Conscious sedation will be used in subjects undergoing liver biopsy. Sedative drugs will be provided by experienced physicians of the NIH CC. Side effects from sedative medications include cardiovascular and respiratory depression manifested by bradycardia, hypotension, respiratory acidosis, and apnea. Additional adverse reactions reported with these drugs are stinging or pain at the injection site, hiccoughs, nausea, vomiting, postoperative drowsiness and headache, and hypersensitivity reactions. Patients will be closely monitored and appropriate countermeasures will be taken as necessary.

MRI: For most subjects, the primary risk associated with MRI is discomfort as subjects will be asked to lie still for a long period of time. Additionally, subjects may find the clicking sound caused by the MRI disturbing. Subjects with pacemakers, aneurysm clips, metallic prostheses, shrapnel fragments, welders and metal workers are at risk for injury and will be excluded from the study.

Blood Draw: Collection of blood may be associated with discomfort, bruising, local hematoma formation and, on rare occasions, infections, lightheadedness, and fainting. The amount of blood drawn for research purposes will be within the limits allowed for adult subjects by the NIH CC (Medical Administrative Policy 95-9: Guidelines for Limits of Blood Drawn for Research Purposes in the Clinical Center: <http://cc-internal.cc.nih.gov/policies/PDF/M95-9.pdf>.

Electrocardiogram: There are no foreseeable risks associated with this procedure.

Transient Elastography: There are no foreseeable risks to these procedures.

7.2. Potential Benefits

Subjects may not receive any benefit from this study. However, there is the potential that a 6-month treatment regimen of eplerenone may result in reductions of intramyocardial lipid content, hepatic steatosis, and visceral adipose tissue, thereby improving overall cardiovascular health. If this study is successful, then we will develop a larger trial to evaluate the clinical utility of eplerenone in HIV-infected individuals with steatosis.

8. Research Use of Stored Human Samples, Specimens, or Data

- **Intended Use:** Samples and data collected under this protocol may be used to study HIV infection and related disorders. No genetic testing will be performed.
- **Storage:** Access to stored samples will be limited using either a locked room or a locked freezer. Samples and data will be stored using codes assigned by the investigators. Data will be kept in password-protected computers. Only investigators will have access to the samples and data.
- **Tracking:** Samples and data acquired as part of this protocol will be tracked using the CRIMSON database system.
- **Disposition at the Completion of the Protocol:**
 - In the future, other investigators (both at NIH and outside) may wish to study these samples and/or data. In that case, Institutional Review Board (IRB) approval must be sought prior to any sharing of samples and/or data. Any clinical information shared about the sample would similarly require prior IRB approval.
 - At the completion of the protocol (termination), samples and data will either be destroyed, or after IRB approval, transferred to another existing protocol.
- **Reporting the Loss or Destruction of Samples/Specimens/Data to the IRB:**
 - Any loss or unanticipated destruction of samples or data (for example, as a result of freezer malfunction) that meets the definition of Protocol Deviation and/or compromises the scientific integrity of the data collected for the study, will be reported to the NIAID IRB.
 - Additionally, subjects may decide at any point not to have their samples stored. In this case, the principal investigator will destroy all known remaining samples and report what was done to both the subject and to the IRB. This decision will not affect the subject's participation in this protocol or any other protocols at NIH.

9. Remuneration Plan for Subjects

Eligible subjects will receive partial remuneration from the NIH for immediate costs associated with study-related expenses (eg, transportation and lodging) according to established NIH/NIAID guidelines. Subjects will also be compensated for the time and inconvenience of study participation according to the attached schedule (see Table 1). Thus, compensation may be up to \$1280 for completion of the entire study, commensurate with the time and inconvenience of study participation including blood draws, liver biopsy, and scans. If a subject returns for

additional study related procedures as noted in section 6.5, they will be compensated at a rate consistent with the remuneration table.

Table 1 Remuneration			
Visit/Procedure	Hours per Visit (Compensation)	Inconvenience Units (Compensation)	Total Compensation per Visit
Screening visit(s): Screening labs, history/physical, MRI,(brief), anthropometrics transient, elastography	4 (\$50)	8 (\$80)	\$130
Screening visit 2: MRI (full) and DEXA	4(\$50)	7(\$70)	\$120
Screening optional liver biopsy	7 (\$80)	22 (\$220)	\$300
Day 0: History/physical, labs, education start eplerenone	3 (\$30)	2(\$20)	\$50
Weeks 1, 2, 4, 8, 12, 18: History/physical, adherence, labs	2 (\$20) per visit 10 (\$100) total	1 (\$10) per visit 5 (\$50) total	\$30 per visit \$180 total
Week 24: History/physical and labs, DEXA, MRI, elastography, anthropometrics	5 (\$60)	12(\$140)	\$200
Week 24 optional liver biopsy	7 (\$80)	22 (\$220)	\$300
TOTAL COMPENSATION FOR COMPLETE STUDY PARTICIPATION			\$1280
DEXA = dual-energy x-ray absorptiometry; MRI = magnetic resonance imaging; Note: Screening visit and final visit at week 24 may be scheduled over multiple days for subject's convenience.			

10. Assessment of Safety

10.1. Toxicity Scale

The Investigator will grade the severity of each AE according to the “Division of Aids Table for Grading the Severity of Adult and Pediatric Adverse Events” Version 2.0, November 2014, which can be found at:

http://rsc.techres.com/Document/safetyandpharmacovigilance/DAIDS_AE_GRADING_TABLE_v2_NOV2014.pdf

Some grade 1 lab parameters on the DAIDS Toxicity Table (fibrinogen, potassium [low], uric acid [males only, elevated]) fall within the NIH lab reference range for normal values. These normal values will not be reported as grade 1 AEs. The grade 1 values for these tests will be reported as follows:

- Fibrinogen: 100-176 mg/dL
- Potassium (low): 3.0-3.3 mmol/L

- Uric acid (males): 8.7-10.0 mg/dL
- Magnesium (low): 0.60-0.65 mmol/L

10.2. Recording/Documentation

At each contact with the subject, information regarding AEs will be elicited by appropriate questioning and examinations. All AEs, both expected/unexpected and related/unrelated will be recorded on a source document.

Source documents will include progress notes, laboratory reports, consult notes, phone call summaries, survey tools, and data collection tools. Source documents will be reviewed in a timely manner by the research team. All reportable AEs that are identified will be recorded in CRIMSON. The start date, the stop date, the severity of each reportable event, and the PI's judgment of the AE's relationship and expectedness to the study agent/intervention will also be recorded in CRIMSON.

10.3. Definitions

Adverse Event: Any untoward medical occurrence in a human subject, including any abnormal sign, symptom, or disease, temporally associated with the subject's participation in research, whether or not considered related to the research.

Serious adverse event (SAE): Any AE that results in one or more of the following outcomes:

- death;
- a life-threatening event (places the subject at immediate risk of death from the event as it occurred);
- an inpatient hospitalization or prolongation of existing hospitalization;
- a persistent or significant incapacity or substantial disruption of the ability to conduct normal life functions;
- a congenital anomaly/birth defect;
- on the basis of appropriate medical judgment, may jeopardize the subject's health and may require medical or surgical intervention to prevent one of the other outcomes listed in this definition. (Examples of such events include allergic bronchospasm requiring intensive treatment in the emergency room or at home, blood dyscrasias or convulsions that do not result in inpatient hospitalization, or the development of drug dependency or drug abuse)

Protocol Deviation: Any change, divergence, or departure from the IRB-approved study procedures in a research protocol. Protocol deviations are designated as serious or non-serious and further characterized as

1. Those that occur because a member of the research team deviates from the protocol
2. Those that are identified before they occur, but cannot be prevented
3. Those that are discovered after they occur

Serious Protocol Deviation: A deviation that meets the definition of an SAE or compromises the safety, welfare, or rights of subjects or others.

Non-compliance: The failure to comply with applicable NIH Human Research Protections Program (HRPP) policies, IRB requirements, or regulatory requirements for the protection of human subjects. Non-compliance is further characterized as

1. Serious: Non-compliance that
 - a. Increases risks, or causes harm, to subjects
 - b. Decreases potential benefits to subjects
 - c. Compromises the integrity of the NIH-HRPP
 - d. Invalidates the study data
2. Continuing: Non-compliance that is recurring
3. Minor: Non-compliance that, is neither serious nor continuing.

Unanticipated Problem (UP): Any incident, experience, or outcome that meets all three of the following criteria would be considered a serious UP:

1. unexpected in terms of nature, severity, or frequency in relation to
 - a. the research risks that are described in the IRB-approved research protocol, informed consent document, package insert, or other study documents; and
 - b. the characteristics of the subject population being studied
2. possibly, probably, or definitely related to participation in the research
3. suggests that the research places subjects or others at a greater risk of harm (including physical, psychological, economic, or social harm) than was previously known or recognized.

Unanticipated problem that is not an Adverse Event (UPnonAE): An unanticipated problem that does not fit the definition of an AE, but that may, in the opinion of the investigator, involve risk to the subject, affect others in the research study, or substantially impact the integrity of

research data. These events may involve a greater risk of social or economic harm to subjects or others rather than physical/psychological harm. Such events would be considered a non-serious UP. Examples of a UPnonAE include a breach of confidentiality, accidental destruction of study records, or unaccounted-for study drug.

10.4. Reporting Procedures

10.4.1. Expedited Reporting to the NIAID IRB

Serious and non-serious UPs, deaths, serious deviations, and serious or continuing non-compliance will be reported within 7 calendar days of investigator awareness. SAEs that are possibly, probably, or definitely related to the research will be reported to the NIAID IRB within 7 calendar days of investigator's awareness, regardless of expectedness.

10.4.2. Waiver of Reporting Anticipated Protocol Deviations, Expected non-UP AEs, and Deaths

Anticipated deviations in the conduct of the protocol will not be reported to the IRB unless they occur at a rate greater than anticipated by the study team. Expected AEs will not be reported to the IRB unless they occur at a rate greater than that known to occur in HIV-infected patients. If the rate of these events exceeds the rate expected by the study team, then the events will be classified and reported as though they are UPs. Deaths related to the natural history of HIV infection will be reported at the time of continuing review.

10.4.3. Annual Reporting to the NIAID IRB

The following items will be reported to the NIAID IRB in summary at the time of Continuing Review:

- Serious and non-serious unanticipated problems
- Expected SAEs that are possibly, probably, or definitely related to the research
- SAEs that are not related to the research
- All AEs, except expected AEs granted a waiver of reporting
- Serious and non-serious protocol deviations
- Serious, continuing, and minor non-compliance
- Any trends or events which in the opinion of the investigator should be reported

10.5. Reporting of Pregnancy

In the event of pregnancy:

- Discontinue the study agent and procedures but continue to follow-up over the phone for safety and outcomes
- Report to the IRB
- Advise research subject to notify the obstetrician of study participation and study agent exposure

10.6. Type and Duration of the Follow-up of Subjects after Adverse Events

AEs that occur from the time of enrollment of the subject are followed until the final outcome is known or until the end of the study follow-up period.

SAEs that have not resolved by the end of the follow-up period are followed until final outcome is known. If it is not possible to obtain a final outcome for an SAE (eg, the subject is lost to follow-up), then the reason a final outcome could not be obtained will be recorded by the investigator.

10.7. Pausing Rules for an Individual Subject

Pausing is the suspension of administration of study agent to a single subject until a decision is made whether or not to resume administration of the study agent.

The pausing criteria for a single subject in this study include any of the following:

- A subject experiences an SAE that is unexpected and possibly, probably, or definitely related to eplerenone
- A subject develops a potassium level > 5.5 meq/L, eGFR < 60 mL/min/1.73 m², or serum creatinine > 1.5 mg/dL
- Any safety issue that the investigator determines should pause administration of a study agent to a single subject

10.7.1. Resumption Following a Pause for a Single Subject

The PI will determine whether or not it is safe to resume administration of the study agent to the subject.

- Subjects who develop a potassium level > 5.5 meq/L, eGFR < 60 mL/min/1.73 m², or serum creatinine > 1.5 mg/dL will be asked to return to clinic in 24-48 hours for repeat lab testing.
- Subjects will only continue/resume treatment if an alternative cause for these lab abnormalities is identified and the abnormality resolves.

A subject who does not resume eplerenone will continue to be followed for safety.

10.8. Halting Rules for the Protocol

Halting the study requires immediate discontinuation of study agent administered for all subjects and suspension of enrollment until a decision is made whether or not to continue enrollment and study agent administration.

The halting rules are:

- Two or more subjects experience the same or similar SAEs that are unexpected and are possibly, probably, or definitely related to eplerenone

OR

- any safety issue that the PI determines should halt the study

The PI will determine if the study should be halted. The NIAID IRB may also halt the study.

10.8.1. Reporting a Study Halt

If a halting rule is met, then a description of the AE(s) or safety issue must be reported by the PI, within one business day, to the IRB by fax or email.

10.8.2. Resumption of a Halted Study

The PI will determine if it is safe to resume the study. The PI will notify the IRB of the decision on resumption of the study.

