10.11. Safety Monitoring Plan

The data gathered during this study will be monitored by the PI for safety and compliance with protocol-specified requirements.

11. Statistical Considerations

The proposed study is designed as a proof-of-concept study and will employ paired comparison of each subject pre- and post-treatment. With a total of 20 subjects we will have 90% power to detect a 0.1% unit change in intramyocardial lipid content based on an estimated within subject standard deviation of MRS intramyocardial lipid of 0.07% reported by O'Connor and colleagues³⁶. In our prior work, HIV-infected subjects had a mean intramyocardial lipid content of 1.5% whereas controls were 1.0%. Therefore, with this sample size we will have ample power to detect a minimal clinically relevant reduction of 0.3% units or greater following eplerenone therapy.

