12.2. Subject Confidentiality

All records will be kept confidential to the extent provided by federal, state and local law. The study monitors and other authorized representatives of the Sponsor may inspect all documents and records required to be maintained by the Investigator, including but not limited to, medical records. Records will be kept locked and all computer entry and networking programs will be done with coded numbers only. Clinical information will not be released without written permission of the subject, except as necessary for review by IRB or the OHRP.

13. Data Handling and Record Keeping

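### Section 10.8.2 lets the PI restart a halted study on the PI's own decision, so nothing makes re-dosing wait for independent review after the SAE halting rule is met

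*Combined protocol and SAP*

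**What the plan says.** Section 10.8 defines a halt as "immediate discontinuation of study agent administered for all subjects and suspension of enrollment until a decision is made". There are two triggers. One is two or more subjects with the same or similar unexpected SAEs that are at least possibly related to eplerenone. The other is any safety issue for which the PI thinks a halt is needed. The PI decides whether to halt, and the section adds: "The NIAID IRB may also halt the study".

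Under Section 10.8.1, once a halting rule is met, a description of the event "must be reported by the PI, within one business day, to the IRB".

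Section 10.8.2 is the whole resumption rule, in two sentences: "The PI will determine if it is safe to resume the study" and "The PI will notify the IRB of the decision on resumption of the study".

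Safety monitoring is covered in Section 10.11: "The data gathered during this study will be monitored by the PI for safety and compliance with protocol-specified requirements". Section 12.2 mentions others who may look at the data ("The study monitors and other authorized representatives of the Sponsor may inspect all documents and records"), but gives them no part in resumption. No data monitoring board or independent medical monitor is given a role.

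**The concern.** The SAE trigger in Section 10.8 describes a pattern of unexpected, drug-related serious events that may bear on everyone taking eplerenone. Agreement from someone other than the PI is most useful at that moment. As written, the PI rates relatedness and expectedness (Section 10.2), decides on the halt, monitors safety and decides on the restart. The IRB is told of the last decision but need not have agreed to it, and need not have heard of it before tablets are taken again. At stake is the re-exposure of the subjects then on treatment before any independent body has reacted to the events that caused the halt.

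**Working it through.** The main question is one of authority, so the check is to set the relevant sections side by side. The plan states no figure on this point to reproduce.

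**1. Who decides, and when the IRB hears**
- Halt: the PI, or the IRB (10.8).
- Report of the halt: one business day (10.8.1).
- Report of related SAEs: "SAEs that are possibly, probably, or definitely related to the research will be reported to the NIAID IRB within 7 calendar days" (10.4.1).
- Decision to resume: the PI (10.8.2).
- Notice of resumption: no deadline, and no stated order relative to dosing (10.8.2).

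The one-business-day limit applies to the halt and not to the restart. A notice sent after re-dosing would therefore comply.

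**2. IRB-imposed halts.** Section 10.8.2 is worded for any halted study. It has no separate rule for a halt that the IRB called under 10.8.

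**3. Contrast with a single-subject pause.** Section 10.7.1 also leaves resumption to the PI. For potassium above 5.5 mEq/L, eGFR below 60 mL/min/1.73 m² or creatinine above 1.5 mg/dL, however, it requires repeat testing in 24 to 48 hours, and treatment continues only if another cause is found and the abnormality clears. Section 10.8.2 sets no criterion of this kind for the whole study.

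**4. How many subjects could be re-exposed.** The ceiling is the planned 20, if all are on drug at once. For a more likely number:
- The Protocol Summary gives December 2015 to February 2018, about 26 months, and about 7 months per subject. That leaves roughly 19 to 20 months for entry.
- Dosing lasts 24 weeks, about 5.5 months (Section 5.3).
- Assuming even accrual, the number on drug at one time is 20 × 5.5 / 19.5 = 5.6, so about 5 to 6.

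The accrual ceiling of 50 is not a count of subjects treated at the same time and does not bear on this.

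**5. What a wait for the IRB would cost in exposure.** From Section 5.3, the planned course is 24 × 7 = 168 days. The planned dose is 25 × 7 + 50 × 161 = 175 + 8,050 = 8,225 mg. For extra time off drug at 50 mg/day, not made up:

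| Delay | Share of days | Share of dose |
|---|---|---|
| 1 week | 7/168 = 4.2% | 350/8,225 = 4.3% |
| 2 weeks | 14/168 = 8.3% | 700/8,225 = 8.5% |
| 4 weeks | 28/168 = 16.7% | 1,400/8,225 = 17.0% |

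The documents give no IRB review time, so the delays are an assumed range. That doses are not made up is also an assumption. Section 6.4 places the final visit after the full regimen is complete, which can be read as moving Week 24 after an interruption. On that reading no dose is lost.

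**The case against.** The strongest case against is that several safeguards already stand between a halt and unsafe re-dosing.

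- **The IRB is informed and can act.** It has the halt report within one business day and may then impose its own halt. A reader might infer that the IRB is shut out of the process, and the documents do not support that. The exposed case is a restart by the PI before the IRB has acted on the report.
- **An IRB halt is not open to override.** Because 10.8.2 covers any halt, a reader might infer that the PI may lift one imposed by the IRB. Section 10.3 counts failure to comply with IRB requirements as non-compliance, and as serious if it increases risk to subjects. Section 10.4.1 makes serious non-compliance reportable within 7 calendar days. On a fair reading, dosing against an IRB halt would breach the protocol's own terms. What remains is a gap in drafting: no sentence says who lifts such a halt.
- **Individual pausing still applies.** Sections 10.7 and 10.7.1 continue to block re-dosing of subjects with the listed potassium, eGFR or creatinine abnormalities. Hyperkalemia and raised creatinine are the events that Section 7.1 reports as more frequent on eplerenone in one trial. A restart therefore does not re-expose every subject regardless of condition. These rules have no laboratory bar for other kinds of SAE, where the PI again decides.
- **IRB agreement after every halt would go too far.** It could discourage the PI from calling a precautionary halt, and eplerenone is a marketed drug with overall adverse event rates similar to placebo in the trials that Section 7.1 describes.

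All four points stand as limits on the concern. None of them makes a restart wait for independent review once the SAE rule has been met.

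**Conclusion.** The point holds in a limited form and is worth a cheap improvement. Section 10.8.2 is a stated rule. It lets the person who conducts and monitors the study resume dosing on that person's own decision, with notice to the IRB at no fixed time. The gap matters chiefly after the SAE halting rule is met, and secondarily because halts imposed by the IRB are not set apart.

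The number re-exposed is the number on drug at the time: at most 20, and about 5 to 6 under the assumption of even accrual. The probability of a halt cannot be estimated from the documents. A reader might infer that up to 50 subjects are at risk, or that IRB consent should precede resumption after every precautionary halt. The documents support neither. IRB policy outside the protocol may also govern who lifts an IRB halt, but the protocol does not say so.

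**What to change.** Replace Section 10.8.2 with three sentences:

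> After a halt triggered by the SAE halting rule, dosing and enrolment resume only after the IRB has agreed to the PI's recommendation. After any other halt called by the PI, the PI notifies the IRB in writing, with the reasons, before dosing restarts. A halt imposed by the IRB is lifted only by the IRB.

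This needs an amendment to one short section. It changes no endpoint, sample size, visit or analysis, and the PI can still halt at once. A precautionary halt called by the PI would need only prior notice, which keeps the disincentive small.

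The cost arises only if an SAE-triggered halt occurs: subjects stay off drug while the IRB reviews. If missed doses are not made up, this could slightly reduce exposure before the pre/post comparison in Section 11.1, at the weekly rate of about 4% shown above.
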